# Please save frequently

- e) State if deception (including incomplete disclosure of study purpose/procedures) will be used. If so, describe the nature of the deception and provide a rationale for its use. Also, describe debriefing procedures or justify a waiver of the requirement to debrief. NOTE: for studies using deception, an alteration of consent must be justified in the Informed Consent section of the protocol (#13) and the debriefing script/statement must be uploaded in the Attachments section (#16). See IRB Deception Guidelines.
- f) Is there an accepted standard of care and/or standard practice at SLU for the Y condition/disease/situation being studied? This information will assist in comparing the risk/benefit ratio of study procedures relevant to usual care that would be received outside of the research context. \*?HELP?\*

If yes, please describe the standard of care and standard practice at SLU for the

е -Ркотс	PROTOCOL Biomedical Research Saint Louis University	Protocol # 25138 [name]
Protocol Title:	Shear wave sonoelastography for the noninvasive evaluation of hepati pediatric population	
	condition/disease/situation being studied.	1.1
	The current standard of care for evaluation of pediatric patients with liver disease inc routine abdominal ultrasounds and liver biopsy in order to determine the stage of fibr	
g)	Does this study involve any diagnostic imaging, labwork or genetic testing that could result in clinical discovery (diagnoses, genetic mutations, etc.)? Note that this could include discovery that is expected (related to the research) or incidental (not related to research aims, but possible, like a mass/shadow found in imaging despite not looking for it).	Ν
	If yes, please describe and include whether there are plans to share findings with stu participants.	ldy
h)	Is this study subject to the NIH Genomic Data Sharing Policy?	Ν
	The NIH GDS policy applies to all NIH-funded research that generates large-scale human genomic data as well as the use of these data for subsequent research and includes: genome-wide association studies (GWAS), single nucleotide polymorphisms (SNP) arrays, and genome sequence, transcriptomic, metagenomics, epigenomic and gene expression data, irrespective of NIH funding mechanism. Click here for more specific examples.	
	* * * Radioisotopes or Radiation Machines * * *	
You have not se information, plea	elected the Radioisotopes option in the General Checklist. If you would like to add Rad ase select the option to enable this section.	ioisotopes

#### 4. Radioisotopes or Radiation Machines

In this section, investigators must enter all radiation usage associated with the protocol.

Important: Protocols that involve non-standard of care radioactive materials (which includes the terms "radioisotopes", "radionuclides", "radiopharmaceuticals", and "nuclear medicine studies", e.g., "PET", "MUGA", "Zevalin", and/or specific radionuclides such as "F-18", "Tc-99m", "Th-201", "I-131", "Ra-233", "Y-90", etc.) will receive review by the Radiation Safety Officer (RSO) and/or Radiation Safety Committee (RSC). In these cases, submission to the RSO/RSC should occur first, even before submission to IRB. For more information on how to submit for radiation safety review, see RSC instructions or contact the Radiation Safety Officer at [name].

(1) It is the responsibility of the PI to assure the accuracy and completeness of the data submitted in this section, consistent with guidelines provided below. (2) For projects requiring radiation procedures, please refer to this guidance.

a) If applicable, list and quantify the radiographic diagnostic and therapeutic procedures associated with this protocol by clicking "Add" and adding to Table 1 below. (Includes X-ray, fluoroscopy, CT, radioactive materials, nuclear medicine, PET-CT, radiation oncology, accelerator, Cyber Knife procedures, etc.)

C-PROTOCOL Biomedical Research Saint Louis University	Protocol # 25138 [name]
Protocol Title: Shear wave sonoelastography for the noninvasive evalu pediatric population	ation of hepatic fibrosis in the
b) Total estimated research radiation dose * :	
* Calculate from the table above by adding the Effective Dose Subtotals for all procedur	es.
NOTE: Informed Consent Radiation Exposure Risk Statement- The applicant must inse	
Informed Consent Radiation Exposure Risk Statement template language into the SLU inclusive of applying the total estimated research radiation dose specified in item b) from instructed in the SLU INPR Information Consent Template Context the ISP Office at 077.7	n the table above, as
instructed in the SLU IRB Informed Consent Template. Contact the IRB Office at [name] any questions.	44 of [contact] with
5. Devices	
a) Please list in the space below all investigational devices to be used on subjects duri	on this study
	ig uns study.
b) Please list in the space below all FDA approved devices to be used on subjects duri	a this study
	ig this study.
FDA Approved Devices	
of IDI impri	de IDE #. Documentation E # required unless nted on sponsor protocol h in section #16).
System has F	gnificant risk. The device DA approval for use in and now in children as

 
* * * Drugs, Reagents, Chemicals, or Biologic Products * * *
 
6. Drugs, Reagents, Chemicals, Biologic Products, or Dietary Supplements, Vitamins, a
 
	nd Other Food Agents

C-PROTOCOL		PROTOCOL Biomedical Research Saint Louis University	Protocol # 25138 [name]
Pro	otocol Title:	Shear wave sonoelastography for the non pediatric population	ninvasive evaluation of hepatic fibrosis in the
	Phase III	Phase IV	Not Phased
	List placebo if it is consi is considered a drug than need to be listed.	idered a drug (contains more than inactive i at should be listed, whereas placebo tablets	ingredients). For example, normal saline are usually inert ingredients that do not
b)	Please list in the space subjects during this stud	below all investigational drugs, reagents or dy. Attach all applicable Investigator Brochu	chemicals to be administered to ures in section #16 (Attachments).
c)	Please list in the space during this study. Attack	below all FDA approved drugs, reagents, c all applicable package inserts in section #	hemicals to be administered to subjects 16 (Attachments).
d)	Please list in the space subjects during this stud	below all dietary supplements, vitamins, mi dy.	inerals, or foods to be administered to
Plea	se read the IND Stateme	ents.	
		* * * Other Levels Of Review * * *	•
7. Ot	ther Levels Of Review		
	1. University Radiation	Safety	
	"radioisotopes", "radi "MUGA", "Zevalin", a "Y-90", etc.) will rece Committee (RSC). Fo	e non-standard of care radioactive materials onuclides", "radiopharmaceuticals", and "nu ind/or specific radionuclides such as "F-18" ive review by the Radiation Safety Officer ( or information on how to submit for radiation Safety Officer at [name].	uclear medicine studies", e.g., "PET", ', "Tc-99m", "Th-201", "I-131", "Ra-223", RSO) and/or Radiation Safety
	X Not Applicat	ble	
	Yes, study ir	nvolves radioactive materials (per instructio	ns, submit to RSC before IRB)
	2. Institutional Biosafety	,	
	Gene Transfer), or D Microorganisms cont (including select age Service (APHIS)) into Safety Officer. Most of	g the deliberate transfer of Recombinant or NA or RNA derived from Recombinant or S aining Recombinant or Synthetic Nucleic A nts and toxins as defined by CDC and/or A o one or more human research participants of these protocols also require review and a (IBC). Please contact the SLU Biological S	Synthetic Nucleic Acid Molecules, or cid Molecules and/or infectious agents nimal and Plant Health Inspection must be reviewed by the SLU Biological approval by the SLU Institutional

Protocol Title:

Shear wave sonoelastography for the noninvasive evaluation of hepatic fibrosis in the pediatric population

\_\_\_\_\_

information.

X Not Applicable
 Yes, study requires Institutional Biosafety review

#### 3. Pharmacy, Therapeutics, Nutrition, and Transfusion (PTNT) Committee

Saint Louis University Hospital requires that all research involving the administration of medications within the hospital (including outpatient areas such as the Emergency Department, Outpatient Center, Saint Louis University Hospital-South Campus, etc.) be reviewed and approved by the Pharmacy, Therapeutics, Nutrition, and Transfusion (PTNT) Committee and that study drugs are received, stored, prepared, and dispensed by the Hospital's Department of Pharmacy Services. Please contact the Investigational Drug Services Clinical Pharmacist at [name] or [contact] for more information.

#### X Not Applicable

Yes, study requires PTNT review

#### 4. Saint Louis University Hospital

All research involving Saint Louis University Hospital, including the Emergency Department, inpatient or outpatient services (including outpatient surgery at ABI and the infusion center at DOB) and medical record access, requires approval from the Saint Louis University Hospital Research Review Committee prior to study initiation. This process is designed to facilitate compliance with state and federal regulations as they pertain to research in hospitals and clinical research billing. Documents should be submitted as soon as possible, or at the latest, concurrently with IRB submission. Please contact the Research Compliance Office at [name] or [contact] of the SLU Clinical Trials Office (CTO) at [name] or [contact] for more information.

#### X Not Applicable

Yes, study requires Saint Louis University Hospital review

#### 5. SSMSL

All research involving SSMSL locations (including Cardinal Glennon), including inpatient or outpatient services and medical record access, requires approval from the SSM STL or SSM Cardinal Glennon Research Business Review (RBR) prior to study initiation. This process is designed to facilitate compliance with state and federal regulations as they pertain to research in hospitals and clinical research billing. While researchers can begin to complete the SSM RBR form at any time, the form should not be submitted until the IRB and the CTO have approved the study. Please contact the SSMSL Office at [name] or [contact] for more information.

#### Not Applicable

X Yes, study requires RBR review

e	<del>)</del> -P	ROTOCOL	PROTOCOL Biomedical Research Saint Louis University		Protocol # 25138 [name]
Pro	otoc	ol Title:	Shear wave sonoelastography for the noninvasive er pediatric population	valuation of hepation	c fibrosis in the
	6.	the NIH GCP Training Registration may be FDAAA definition of ClinicalTrials.gov. 2) behavioral "Clinical require personnel or Registering may be definitions here. Cor registering on Clinica	quire registration on ClinicalTrials.gov, and/or is this p ng Requirement? (Select "Yes" if either apply) required if any of the following apply: 1) The project n an "Applicable Clinical Trial", which requires registration As of January 1, 2017, a new NIH policy mandated b Trials" to be registered on ClinicalTrials.gov. In addition In NIH "Clinical Trials" to take GCP training every three required for Journal Publication (ICMJE). Please revie intact the CTO at [contact] with que alTrials.gov and refer to the training page of the IRB w GCP Training requirements.	neets the on on iomedical and n, NIH policies years. 3) w relevant stions about	,
 8. S (incl a)	udé Ex	description of each gi	* * * Subject Population * * * space below, please detail the participants that you a oup requested) subjects. (For example $\geq$ 18 yrs to 90 yrs).	re requesting to re	cruit
b)	Nu		ojects to be accrued at SLU or SLU site (this includes a of the SLU PI).	all 200	
	par	ceeding the number lis ticipants are to be acc scribed in 3d.	sted here is a protocol violation. Prior IRB approval is protocol violation. Prior IRB approval is protocol. If applicable, this number should be consistent v	required if addition with your power an	al alysis
c)	Nu	mber of evaluable sub	pjects to be accrued study wide. *?HELP?*	200	
d)	ec co re: Cli mi Tl	conomically or educationsent for themselves) search, and 2) specify ick on hyperlinks to ac itigating risks. he study is specifically	opulations (minors, pregnant women and fetuses, neo onally disadvantaged, prisoners, adults temporarily or : 1) provide the rationale for the importance of includir the measures being taken to minimize risks to potent ccess SLU Guidelines containing additional considerat	permanently unab ng this population in ially vulnerable sub ions and strategies e elastography in d	le to n the ojects. s for etermining
	ar	nd non-radiation base	patients. The shear wave elastography exam has no d imaging test. There are no risks to the patients. Ro formed in these patients is part of standard of care trea	utine ultrasound ex	
e)	ap int	plicable. Examples fo	minors are not included, a clear compelling rationale r r not including minors: disease does not occur in child with and development; etc. If federally funded reference . *?HELP?*	ren; drug or device	e would

Protocol Title:

Shear wave sonoelastography for the noninvasive evaluation of hepatic fibrosis in the pediatric population

If minors are of age of assent but are mentally unable to provide consent, parental consent will be obtained. The minor will be made aware of the study to the best of our ability and the decision will be left up to the parents at that point. Parents will be clearly be made aware that the age of the child would normally require their assent but because of the education level of their child the assent is not obtained.

\_\_\_\_\_

- f) If any specifically targeted subjects are students, employees, or laboratory personnel, specify the measures being taken to minimize the risks and the chance of harm to these potentially vulnerable subjects. See SLU Guidelines for additional considerations and strategies for mitigating risks.
- g) Describe how potential subjects will be identified for recruitment (e.g., chart review, referral from individual's treating physician, those individuals answering an ad). How will potential participants learn about the research, and how will they be recruited (e.g., flyer, e-mail, web posting, telephone, etc.)? Upload recruitment materials in the Attachment Section (#16). Important to remember: potential subjects cannot be contacted before IRB approval. NOTE: The use of SLU owned websites in an approved SLU format (e.g., Cancer Center website, etc.) are always approved methods of recruitment.

Potential subjects with known liver disease will be recruited by the pediatric gastroenterologists as these patients would be undergoing ultrasound evaluation and liver biopsy as part of standard of care treatment. These patients would be presented with a recruitment statement form during their clinic visit. During their exam in radiology, explanation of the procedure would be performed by the radiologist who would then obtain consent from the parent and informed assent from the child. Potential control patients will be recruited by giving them a recruitment statement and copy of the consent form as they check-in to the radiology department for an abdominal exam ordered by a physician as part of standard clinical care. The form will inform them that they may be asked to participate in the study following the exam. If deemed eligible by the radiologist, the radiologist will then obtain consent from the parent and informed assent from the child. Recruitment will also occur via flyers posted in the radiology department and GI clinics.

\_\_\_\_\_

\* \* \* Subject Population \* \* \*

8. Subject Population (continued) Page numbers from a sponsor's protocol/grant may be referenced in 8h.

h) Inclusion and Exclusion Criteria.

Identify inclusion criteria.

Inclusion criteria:

Test population: Any pediatric patient (0-18 years of age) with known liver disease with plans to undergo a liver biopsy within 1 month of ultrasound exam. Underlying diagnoses include but are not limited to biliary atresia, congenital fibrosis-cholestasis, Alagille syndrome, Caroli's disease, choledochal cyst, alpha-1-antitrypsin deficiency, progressive familial intrahepatic cholestasis (PFIC), viral hepatitis, glycogenosis, fructosemia, Wilson disease, cystic fibrosis, autosomal recessive polycystic kidney disease (ARPCKD), mesenterico-caval shunt, post liver transplant, and nonalcoholic steatohepatitis (NASH). Written informed consent from parent or legal guardian. Informed assent from the child.

Control population: Any pediatric patient (0-18 years of age) undergoing an abdominal ultrasound for reasons other than liver disease and in whom the US shows a normal liver, gallbladder, pancreas, spleen, and biliary tree. Written informed consent from parent or legal guardian. Informed assent from the child. In addition, the patients that have undergone biopsy and have shown no histologic evidence

Protocol Title:

Shear wave sonoelastography for the noninvasive evaluation of hepatic fibrosis in the pediatric population

of fibrosis will also serve as a control population. The elastography measurements of these patients will be compared to those obtained in the pediatric patients without a history of liver disease in whom the ultrasound exam of the abdomen was found to be normal.

\_\_\_\_\_

#### Identify exclusion criteria.

Exclusion criteria: Inconclusive biopsy results. Patient not cooperative for the ultrasound exam. Failure to give informed consent. No biopsy results within allotted time frame. Poor acoustic window in which to perform sonoelastography.

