	un tot wi	ere are 78 participants and 88 exams in the liver disease group. Within this group, usable due to using the linear probe; 5 exams are unusable because they were sc al of 10 patients had two exams – of which 5 exams were repeated since they were th the linear probe and they returned for another curved exam; another 5 were repe ey had a second biopsy performed. A total of 72 exams in the liver group have usa	reen fails. A e initially done eated becaus
	un tot	ere are 93 control patients and 95 control exams. Within the control group, 12 exa able to be used due to using the linear probe; 2 are unusable since they were scre al of 2 patients had a repeat exam since they came back after initially having an ex ear probe. A total of 79 exams in the control group have usable data.	en fails. A
	So	reen fails include those from patients who moved too much, who were too obese to age, or in whom the liver biopsy was not performed.	o obtain an
14.	ls t	here a Data Safety Monitoring (DSM) plan for this study?	
		Y No	
		Yes, a copy of the DSM report(s) for the last approval period is attached.	
		Yes, but a copy of the DSM reports(s) for the last approval period is not attac explain below.	ched. Please
15.	FD		
		A Regulated Studies Food and Drug Administration (FDA) Regulated Study, (i.e., involves drugs, N	

0 -Protoc	PROTOCOL Biomedical Research Saint Louis University	Protocol # 25138 [name]
Protocol Title:	Shear wave sonoelastography for the noninvasive evaluation of hepatic pediatric population	; fibrosis in the
a)	Have there been any changes in the FDA status of any drug or device used in the study? If yes, please explain:	
b)	Have any of the investigational drugs or devices used in this study received FDA approval? If yes, please explain:	
c)	Have any new alternative drugs or devices been approved for treatment of the study condition that may affect subjects willingness to participate? If yes, please explain:	
	Have current subjects been notified? Please explain:	
d)	Has there been a change in the standard care that may be considered as an alternative to the investigational drug or device or that would affect the original study design? If yes, please explain:	
	Have current subjects been notified? Please explain:	
e)	Is there any new information that might affect the risk/benefit ratio and the willingness of current study subjects to participate or to continue to participate in the research? If yes, please explain:	

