The results of the SWE using the velocity measurements displayed on the elastography map with a quantitative color map that is expressed in kPa (kiloPascals) will be correlated with the stage of fibrosis using the METAVIR scale from the liver biopsy results in order to determine the accuracy of SWE in evaluating the various degrees of liver fibrosis. The statistical analysis will include Receiver Operating Characteristic curves as well as scatter plots and box plots. The mean and median values as well as a range of the SWE measurements will be correlated with the individual METAVIR stages of fibrosis (F0-F4), and a p value will be calculated for each stage to assess the accuracy of SWE based on individual fibrosis stages. Further statistical analysis will also be performed to compare results of SWE and histopathology in subgroups of liver disease patients, such as those with NASH compared to those without. Scatter plots will be used to compare the SWE results in normal patients to those with liver disease.

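### Failed elastography scans are excluded and pooled with missing biopsies, so accuracy will describe completed scans only; the effect on overall liver-group accuracy is small and may be nil, but the plan would not show it

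*Combined protocol and SAP*

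**What the plan says.** **Exclusions.** Section 8(h) lists a child who does not cooperate with the ultrasound and "Poor acoustic window in which to perform sonoelastography". The same list contains inconclusive biopsy results and biopsy results not available in time.

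**Progress report.** Continuing Review, item 13, says that screen "fails include those from patients who moved too much, who were too obese to" be imaged, and adds those "in whom the liver biopsy was not performed". In the liver group (78 participants, 88 exams), "5 exams are unusable because they were" screen fails, with no split by cause. "A total of 72 exams in the liver group have" usable data. In the control group (93 patients, 95 exams), 12 exams were lost to the linear probe and 2 were screen fails. "A total of 79 exams in the control group have usable data".

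**Analysis.** Section 3(d) states: "The statistical analysis will include Receiver Operating Characteristic curves as well as scatter plots and box plots". It adds a p value for each METAVIR stage and subgroup comparisons, "such as those with NASH compared to those without". It gives no technical failure rate, no reporting of failures by reason and no rule for failed scans.

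**Intended use.** The lay summary in section 2(a) presents elastography as something that might remove the need for biopsy.

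**The concern.** Poor cooperation and a poor acoustic window become known only when the scan is attempted. They are results of the index test, used here as eligibility criteria. A biopsy that was not done is a different thing, a missing reference standard. Pooling the two hides how often the test itself gave no reading.

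This matters because of the intended use. A child whose scan gives no reading cannot be staged by elastography, so the frequency of that outcome belongs beside any accuracy figure. Section 1(a) names fibrosis secondary to obesity as a focus and criticises transient elastography as unreliable in obese patients. Yet children too obese to image by the study method would drop out without a planned report. Such failures could fall mainly in the planned NASH subgroup, which rests on fewer exams than the whole group.

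**Working it through.** **Inputs (Continuing Review, item 13).** Liver: 78 participants, 88 exams, 5 screen-fail exams, 72 usable exams, 5 rescans after a linear-probe exam and 5 repeats for a second biopsy. Controls: 95 exams, 12 linear-probe, 2 screen fails, 79 stated as usable. Item 6 gives 9 subjects who failed screening. No accuracy, stage mix or NASH count is given.

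**Check of the counts.**
- Liver linear-probe exams (the number is lost in the text): 88 − 5 − 72 = 11. After 5 rescans, 11 − 5 = 6 patients have only a linear exam.
- Liver patients with usable data: 78 − 6 − 5 = 67, if each screen fail is a separate patient. Adding 5 second-biopsy exams gives 72, which agrees with the report.
- Controls: 95 − 12 − 2 = 81, against 79 stated.
- Screen fails: 5 + 2 = 7 exams, against 9 subjects. Four control screen fails would fit both figures: 95 − 12 − 4 = 79 and 5 + 4 = 9.

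**Technical failure rate, liver group.** Let k be the number of the 5 screen fails that were scan failures. The rate among attempted exams is k/(72 + k).
- k = 0: 0%
- k = 1: 1/73 = 1.4%
- k = 2: 2/74 = 2.7%
- k = 3: 3/75 = 4.0%
- k = 4: 4/76 = 5.3% (exact 95% CI 1.5% to 12.9%)
- k = 5: 5/77 = 6.5% (exact 95% CI 2.1% to 14.5%)

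A biopsy not performed can be a reason for failure only in the liver group, because controls are not enrolled for biopsy. If the report's list describes what happened, at least one of the 5 was a missing biopsy and k is at most 4.

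The exam-level intervals treat exams as independent, although 5 children contributed a second one. Per patient the ceiling is 5/(67 + 5) = 5/72 = 6.9%, or 4/(67 + 4) = 4/71 = 5.6%.

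**Effect on overall proportion correctly classified.** With failures counted as not correctly classified, which is one convention, accuracy p becomes p × 72/(72 + k). The relative fall is k/(72 + k), as listed above. With p = 0.90 (assumed), the result is 0.900 at k = 0, 0.876 at k = 2, 0.853 at k = 4 and 0.842 at k = 5. This does not translate into a change in ROC area.

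**Illustrations on assumed group sizes.**
- NASH, 20 to 30 usable exams assumed: no failures there gives 0%; 2 failures give 2/32 to 2/22, or 6% to 9%; 4 failures give 4/34 to 4/24, or 12% to 17%.
- Sensitivity of 0.90 assumed, with 24 to 36 usable exams at or above the cut-off stage: unchanged if no failure falls there. With 2 failures it becomes 0.90 × 24/26 = 0.83 to 0.90 × 36/38 = 0.85.

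**Control group as an indication.** Control screen fails are probably scan failures: 2/81 = 2.5% (exact 95% CI 0.3% to 8.6%), or 4/83 = 4.8% (1.3% to 11.9%) if there were 4. Applied to 77 liver exams, these rates give about 1.9 or 3.7 failures. The count is uncertain and the groups may differ, so this does not fix k.

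**The case against.** The hypothesis in section 2(b) is that elastography measurements correlate with histology, which requires a measurement. Accuracy in completed scans is a legitimate target under stated exclusions. The progress report already counts unusable exams by group and lists reasons, and BMI is collected (section 11(c)). The effect may be nil, and with so few failures any breakdown is descriptive.

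Most of this stands. The completed-scan ROC analysis need not be replaced, and the information largely exists. What is missing is a stated plan to split and report it, without which a reader could not tell a rate of 0% from one near 6%.

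A reader might also infer more than the documents support:
- **That accuracy is materially inflated, or that the NASH result is biased.** The causes of the 5 liver screen fails are not given, movement is listed as well as obesity, and neither the NASH count nor the stage mix is stated.
- **That all 5 were scan failures.** The list of reasons points to at least one missing biopsy.
- **That 9 against 7 is an error.** One figure counts subjects and the other counts exams, so both could be right; or a single miscount in controls could explain this gap and the 81 against 79.
- **That the ceiling covers every failed attempt.** Children turned away before consent would not be counted.

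**Conclusion.** The point holds as a gap in analysis and reporting. Following the plan gives accuracy for completed, usable scans, with technical failures hidden in a mixed screen-fail category. For overall liver-group accuracy the consequence is small: 0% to 6.5% of attempted exams, probably no more than 5.3%, and possibly nothing. This rests on the reported counts of 72 usable and 5 screen-fail exams, and on the convention that a failed scan counts as not correctly classified. The NASH and sensitivity figures rest on assumed sizes and an assumed 0.90. They show only that a few failures weigh more in a small group. A change is worth making because it is cheap and bears on the intended use, not because a large bias has been shown.

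**What to change.** Only data analysis remains (Continuing Review, item 1; Expedited Paragraphs, category 8(c)), so everything can be done at that stage.

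1. Split the liver screen fails into technical scan failures and missing biopsies. Report the technical failure rate per patient with an exact interval, by reason, and descriptively by BMI, age and NASH status.
2. Where a failed scan has a biopsy result, add a sensitivity analysis of sensitivity and specificity at the chosen cut-offs, with failures counted as not correctly classified. Place it beside the completed-scan ROC result.
3. Before reporting participant flow, reconcile section 3(b), which names a curved and a linear probe, with the progress report, which treats linear-probe exams as unusable (12 control exams and, by subtraction, about 11 liver exams). State which exams form the accuracy set, and describe the liver patients who were not rescanned (about 6).
4. Reconcile 81 with 79 usable control exams, and 9 screen-failed subjects with 7 screen-fail exams. State whether each figure counts subjects or exams.

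The cost is a few extra tables from data already collected (section 11(c)) and a secondary accuracy figure that may be slightly less favourable. No new patients or visits are needed.
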